5. REGISTRATION PROCEDURES

5.1 Identification of subjects:

Patients diagnosed with documented progressive metastatic CRPC disease who are visiting Oncology Clinic at NYPH–Cornell Campus for their standard of care visit, will be approached for recruitment for this study. Investigators or delegates under their direct supervision may perform pre–screening of these potential subjects.

5.2 Consent process

Potential subjects will have a discussion with the investigator/delegate including the rationale for the study, investigational nature of the protocol and study drug and the voluntary nature of participation, potential risks and benefits, alternatives to participation, and study procedures. Individuals will have the opportunity to read the written informed consent document at their leisure (preferably outside of the clinical area for > 1 day) and the opportunity to have questions answered in a private location with the understanding that should they decide not to participate, they will still be able to receive any available standard of care therapy. Potential subjects will also have the opportunity to obtain the advice of their treating physician. Investigators or delegates under their direct supervision will verify the subject’s understanding of the investigational and voluntary nature of the study, the potential risks and benefits, study procedures, and alternatives prior to signing of the written informed consent.

5.3 Central Patient Registration

Subjects will be assigned a sequence number for the protocol and will be centrally registered with the Weill Cornell Medicine (WCM), Division of Hematology and Medical Oncology Clinical Research Office with the following documents:

- a. WCM Patient registration form
- b. First and last page of the fully executed informed consent form (including HIPPA), plus additional pages if checkboxes for correlative studies are required.
- c. Eligibility checklist signed and dated by investigator and research nurse
- d. Documentation of any eligibility waivers granted
- e. Entry of screening information into WCM web-based system

Central registration information is reviewed and entered into the HemOnc centralized research database. Documentation of patient registration will be confirmed prior to release of study agent by nuclear medicine.

6. STUDY PROCEDURES

Screening assessments and study procedures outlined in this section can only be performed after obtaining informed consent. All on-study visits and dosing should be scheduled from Day 1 (date of the first infusion) on the study. It is very important that protocol procedures are performed at the time-points stipulated below. When it is not possible to perform, the study visit at the exact time-point, the visit maybe performed within the acceptable visit window as defined in the visit-specific section below.

After obtaining informed consent from enrolled subject(s), screening and study related treatment procedures will be performed as outlined in **Table 15** and described in detail in **Section 6.1**.

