|---------------------------------------|-------------|-------|-------------------|-----------------|-----------------|
| | 65 | 70 | 70 (35 + 35) | 80 (40 + 40) | 90 (45 + 45) |
| Cumulative Dose (mCi/m ²) | 65 | 70 | 70 (35 + 35) | 80 (40 + 40) | 90 (45 + 45) |
| Platelets Grade 4 | 27% | 56.3% | 40% | 50% | 58.8% |
| Platelet Transfusion | 7% | 41% | 0% | 31.3% | 52.9% |
| Neutropenia Grade 4 | 0% | 37.5% | 0% | 31.3% | 29.4% |
| Febrile Neutropenia | 0% | 2.1% | 0% | 0% | 5.8% |

In addition, fractionated dosing allowed concurrent dosing with myelosuppressive chemotherapy:

ii) Phase I trial of fractionated dose ¹⁷⁷Lu–J591 plus docetaxel/prednisone in men with metastatic castration–resistant prostate cancer (42):

Following progression on primary hormonal therapy, chemotherapy can offer symptomatic improvement as well as incremental survival benefit. However, responses are transient and all men eventually suffer from progression of disease as described above with single–agent anti–PSMA based radioimmunotherapy. The combination of taxane chemotherapy with radiotherapy has been used in several diseases because of the radiosensitizing effects of taxane–based chemotherapy. In addition to favorable results from fractionated RIT and the radiosensitizing effects of taxane–based chemotherapy, it is hypothesized that the additional debulking by chemotherapy will overcome some of the limits imposed by the physical characteristics of ¹⁷⁷Lu. Based upon this theory, a phase I trial of docetaxel and prednisone with escalating doses of fractionated ¹⁷⁷Lu–J591 was initiated. 15 men with median age 69.1 (49.3–80.8) were enrolled. The MTD/RP2D of ¹⁷⁷Lu–J591 was 40 mCi/m²x2 doses (delivered with cycle 3 of docetaxel), with 73.3% showing >50% PSA decline, 80.0% reporting >30% PSA decline, and 86.7% with any PSA decline. Predictable, reversible myelosuppression was seen. Even at the highest dose level, no dose limiting toxicity was observed, with short–term / reversible grade 4 neutropenia in 33% and grade 4 thrombocytopenia in 13%.

Aside from the overall rates of dose limiting toxicity, the combined studies have also consistently demonstrated the kinetics of myelosuppression, with nadir neutrophil and platelet counts 28–32 days following the last administered dose of ¹⁷⁷Lu–J591.

With small–molecule radioligand therapy, both the predicted and reported toxicities are much different. One would predict very little myelosuppression, but if it were to occur, it would be

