- c: Any subject with grade ≥2 neutropenia or thrombocytopenia at Treatment 2 will initially not be eligible to receive the second ¹⁷⁷Lu-J591 / ¹⁷⁷Lu-PSMA-617 infusions. The dose will be held until the toxicity has resolved to grade 1 for a maximum of 2 weeks. If the toxicity has not resolved after 2 weeks, the dose will be discontinued.
- d: CMP (with direct bilirubin in subjects with known Gilbert’s syndrome)
- e: CTC enumeration via CellSearch methodology may be obtained during screening or prior to treatment C1D1
- f: CTC collection for research purposes may be performed during screening or prior to treatment C1D1: two 2.3% sodium citrate “light blue top” tubes
- g: Cell-Free DNA BCT[®] may be obtained during screening or prior to treatment C1D1 and will be whole blood collection in a tube intended for collection, stabilization and transportation of cell-free plasma DNA. 10 mL tube will be used for collecting whole blood for research purposes
- h: Radiographic evaluation will include bone scan, CT/MRI of abdomen/pelvis, and Chest x-ray (CXR waived if CT/MRI includes chest). Following mandatory repeat imaging with Scan/Efficacy visit, continued repeat imaging is recommended approximately 12 weeks until radiographic progression as part of standard care.
- i: Planar/SPECT imaging one week after the ¹⁷⁷Lu-PSMA-617 1st dose infusion in all subjects. Optional imaging will be performed on consenting subjects between D1-D4 and/or prior to treatment #2 on D15.
- j: Survival assessment and relevant medical history to be collected until death
- k: Short-term follow up to be completed q4 weeks following the scan visit until 6 months from the 1st treatment visit. Subjects who are progression-free at 6 months will continue with q4-week labs and q12-week standard imaging per guidelines (as in h above).
- l: PRO = patient reported outcomes = BPI-SF and FACT-P; to be performed at time points specified during treatment phase, then q12 weeks (at imaging time points) during short-term follow up until radiographic progression
- m: serum for immune assays; 1 sample to be collected at any time during screening prior to treatment #1, then again during scan/efficacy visit

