6.1.2. Treatment Phase

The treatment and early monitoring phase comprises of 8 visits spanning over approximately 12 weeks.

Absolute neutrophil counts, platelet counts, bilirubin, transaminases, and serum creatinine must be performed with results available and within range of eligibility criteria within 1 week prior to treatment initiation on C1D1.

Details for each visit are listed below:

6.1.2.1 ^{177}Lu -J591 and ^{177}Lu -PSMA-617 infusion (Treatment 1 Day 1) and (Treatment 2 Day 15 \pm 1 day)

The following procedures must be completed on the day of treatment:

- Targeted Physical Examination with vital signs and weight
- Medical History
- Brief Pain Inventory, FACT-P
- ECOG Performance Status
- CBC with differential and platelet count
- CMP (with direct bilirubin with known Gilbert's syndrome)
- PSA
- LDH
- Intravenous dose of ^{177}Lu -PSMA-617 (Dose based on the Cohort in which the subject is enrolled) and ^{177}Lu -J591
- Adverse event evaluation
- Concomitant medications
- Concomitant procedures
- Planar/SPECT imaging (on D15 prior to treatment in consenting subjects)

As stated above, Absolute neutrophil counts, platelet counts, bilirubin, transaminases, and renal function assessment must be available within 1 week prior to treatment on D1 and meet eligibility criteria.

For treatment #2 (D15), grade ≥ 2 thrombocytopenia or neutropenia within 24 hours of the second dose of ^{177}Lu -PSMA products (Visit 3) requires a subject's treatment to be held until the toxicity has resolved to least grade 1. If the toxicity has not resolved after 2 weeks of monitoring, the subject's ^{177}Lu -PSMA product treatment will be permanently discontinued and will be termed dose-limiting toxicity

6.1.2.2 Imaging visit (Day 8 \pm 1) [optional D1, D4, D15 in consenting subjects]

- Planar/SPECT imaging
- Targeted Physical Examination with vital signs and weight
- Medical History
- Brief Pain Inventory, FACT-P
- ECOG Performance Status
- CBC with differential and platelet count
- CMP (with direct bilirubin with known Gilbert's syndrome)
- Adverse event evaluation
- Concomitant medications

6.1.2.2 Follow-up visits: Follow up Visit 1 (Day 22 \pm 3), Follow up Visit 2 (Day 29 \pm 3), Follow up Visit 4 (Day 57 \pm 3)

- Targeted Physical Examination with vital signs and weight
- Medical History
- Brief Pain Inventory, FACT-P
- ECOG Performance Status
- CBC with differential and platelet count
- CMP (with direct bilirubin with known Gilbert's syndrome)

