- PSA (Follow up visits 2 & 4)
- LDH (Follow up visits 2 & 4)
- Adverse event evaluation
- Concomitant medications

6.1.2.3 Follow-up lab visits: Follow up Visit 3 (Day 43 \pm 3); Follow up Visit 5 (Day 71 \pm 3)

- CBC with differential and platelet count
- CMP (with direct bilirubin with known Gilbert's syndrome)
- PSA
- LDH

Lab visits may be performed at any CLIA certified lab

6.1.3. Efficacy Evaluation (scan) Visit (Day 85 ± 7; note that these study procedures are not expected to occur on a single day)

The following procedures must be completed during the efficacy visit(s):

- Targeted Physical Examination with vital signs and weight
- Medical History
- Brief Pain Inventory, FACT-P
- ECOG Performance Status
- CBC with differential and platelet count
- CMP (with direct bilirubin with known Gilbert's syndrome)
- PSA
- LDH
- Testosterone
- CTC count via CellSearch methodology
- CTC for research
- Cell-Free DNA BCT[®] Research blood sample
- Immune research blood sample
- Same standard radiographic imaging modality as baseline (CT/MRI and bone scan +/- CXR)
- Single intravenous dose of ⁶⁸Ga-PSMA-HBED-CC (5±2mCi or 185±74MBq)
- PET/CT scan will be obtained between 1 and 3 hours post-injection of ⁶⁸Ga-PSMA-HBED-CC
- Adverse event evaluation
- Concomitant medications
- Concomitant procedures

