7. DOSING DELAYS/DOSE MODIFICATIONS

There will be no dosing modifications. Unless there are specific reasons not to do so, all patients who are eligible for the trial will receive 5 ± 2 mCi (185 ± 74 MBq) of ^{68}Ga -PSMA-HBED-CC during the screening visit and the Efficacy/Scan visit. During the treatment phase, the subject will receive ^{177}Lu -J591 + ^{177}Lu -PSMA-617 x 2 doses, 2-weeks apart based on the dose-level/Cohort to which he is assigned. The study chair must clear any dosing delays due to logistical issues (e.g. subject scheduling and/or radionuclide shipping that fall outside of the treatment window).

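### Follow-up blood counts stay tied to Day 1 when dose 2 is late; a delay of 4 to 6 days leaves no permitted count in the expected nadir, so a short grade 4 DLT could go unseen

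*Combined protocol and SAP*

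**What the plan says.** Section 6 anchors the whole calendar to the first infusion: "All on-study visits and dosing should be scheduled from Day 1 (date of the first infusion) on the study". It adds: "It is very important that protocol procedures are performed at the time-points stipulated below". Departures are allowed only within each visit's window.

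Section 6.1.2 plans dose 2 for Day 15 ±1. Follow-up CBCs are on Days 22, 29, 43, 57 and 71, each ±3 days, and the efficacy visit is on Day 85 ±7.

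Dose 2 can be late by two routes:
- **Toxicity hold.** For grade 2 or worse neutropenia or thrombocytopenia, footnote c of Table 15 says "The dose will be held until the toxicity has resolved to grade 1 for a maximum of 2 weeks".
- **Logistics.** Section 7 says "The study chair must clear any dosing delays due to logistical issues" and sets no maximum delay.

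Section 2.7 (part B) reports, across the earlier ¹⁷⁷Lu-J591 studies, "nadir neutrophil and platelet counts 28–32 days following the last administered dose of" that agent. Section 6.2.10 makes any related grade 4 hematologic toxicity a DLT, with no minimum duration. Footnote b of Table 15 requires at least weekly follow-up, but only once a count worse than grade 2 has been seen.

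**The concern.** With dose 2 on Day 15, Visit 3 (Day 43) falls 28 days after it, at the start of the expected nadir. That alignment depends on dose 2 being on time. If dose 2 moves and the visits do not, the nadir slides into the two-week gap between Visits 3 and 4.

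The DLT proportion through the efficacy visit is the Phase I primary endpoint (Section 12.5.1), and Section 2.8 expects red marrow to be dose-limiting. Table 11 reports grade 4 platelets in 40% at 35+35 mCi/m² of ¹⁷⁷Lu-J591 alone. Most cohorts here receive 36.5+36.5 mCi/m² plus a second ¹⁷⁷Lu agent, so grade 4 counts are plausible events. In a 3+3 design one unseen event can change the decision: none instead of one in the first three patients, or one instead of two in six. There is also a direct safety point, since a patient could pass through the nadir with no required count.

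**Working it through.** **1. The plan's own figure.** Escalation probability at true DLT rate p, with q = 1 − p, is q³ + 3pq²·q³. At p = 0.40 this is 0.216 + 3(0.40)(0.36)(0.216) = 0.309, matching the 0.31 in Section 12.1. The rest of that table also reproduces. The table assumes that every DLT is observed.

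**2. Dates.** If dose 2 is d days after Day 15, the nadir covers Day 15 + d + 28 to Day 15 + d + 32, that is Day 43 + d to Day 47 + d. Compare this with the windows Day 40–46 (Visit 3) and Day 54–60 (Visit 4):

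| Delay d | Nadir (study day) | Permitted CBC days inside it |
|---|---|---|
| 0 | 43–47 | 43–46 |
| 3 | 46–50 | 46 |
| 4 | 47–51 | none |
| 5 | 48–52 | none |
| 6 | 49–53 | none |
| 7 | 50–54 | 54 |
| 10 | 53–57 | 54–57 |
| 14 | 57–61 | 57–60 |

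On nominal days neither Day 43 nor Day 57 lies in the nadir for d = 1 to 9. For d = 10 to 14, Day 57 does.

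**3. Existing safeguard.** At d = 4 to 6, the Visit 3 window falls 19 to 27 days after dose 2, before the nadir. A count of grade 2 or better there triggers nothing until Day 54 at the earliest. So the patient at risk is one who is no worse than grade 2 at Visit 3, reaches grade 4, and recovers above grade 4 before Visit 4.

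**4. Illustration of missed episodes.** The documents give no grade 4 duration or grade 3 lead-in, so these are assumed. The nadir is uniform over 28–32 days after dose 2. Grade 4 lasts L days centred on the nadir and is preceded by 3, 5 or 7 days of grade 3. A draw during the lead-in starts weekly draws. An episode is missed if no draw falls inside the grade 4 interval.

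Hand check for d = 7 and L = 7 on nominal days. The nadir is uniform over Day 50–54.
- Day 57 sees the episode if the nadir is at Day 53.5 or later: 0.5/4 = 12.5%.
- Day 43 falls in a 3-day lead-in only if the nadir is at or before Day 49.5, which never happens, so 87.5% are missed.
- With a 5-day lead-in the limit is Day 51.5, which adds 1.5/4 = 37.5%, so 50% are missed.
- With a 7-day lead-in the limit is Day 53.5, so 0% are missed.

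Simulated shares missed, for lead-ins of 3/5/7 days:

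| Delay | L (days) | Visits | Missed |
|---|---|---|---|
| 4–6 days, mean | 7 | nominal | 63% / 17% / 0% |
| 7 days | 7 | spread over windows | 62% / 40% / 16% |
| 1–14 days, mean | 7 | nominal | 29% / 14% / 0% |
| 1–14 days, mean | 7 | spread over windows | 29% / 16% / 7% |
| 1–14 days, mean | 5 | nominal | 57% / 43% / 29% |
| 1–14 days, mean | 10 | nominal | 7% / 0% / 0% |

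With on-time dosing, 7-day episodes are missed 0–1% of the time. For 5-day episodes, on-time dosing on nominal days already misses about 38%, so only the excess is due to delay, and with a 7-day lead-in there is none.

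**5. Effect on escalation.** If a fraction f of patients is delayed and a share m of their DLTs is missed, the apparent rate is p(1 − fm). With p = 0.40, m = 0.29 and f = 0.20 this is 0.40 × 0.942 = 0.377, and the escalation probability is 0.348.

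| m | f = 0.05 | f = 0.10 | f = 0.20 |
|---|---|---|---|
| 0.29 | 0.32 | 0.33 | 0.35 |
| 0.14 | 0.31 | 0.32 | 0.33 |

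The m = 0.29 row is on the high side, because non-hematologic DLTs and DLTs from a hold that never resolves cannot be hidden by CBC timing.

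**The case against.** The dates show when no count is required. They do not show that a DLT is missed. A count outside days 28–32 may still be grade 4, or be grade 3 and start weekly draws. With a long lead-in or a long episode, the miss rate in the model falls to zero. For 5-day episodes with a 7-day lead-in, a 4–6 day delay misses about 8%, against 38% on time, so delay can even help.

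The chain is also narrow. A toxicity hold that resolves within days fits poorly with a nadir four weeks after dosing, which leaves mainly logistical delays of unknown frequency. With 10% of patients delayed, a 40% DLT rate and 14–29% of their DLTs missed, the number hidden across 30 Phase I patients is 30 × 0.10 × 0.40 × 0.14 to 0.29, or about 0.17 to 0.35.

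The 40% platelet figure has milder companions: the same column of Table 11 shows no grade 4 neutropenia and no platelet transfusions, and the docetaxel combination had 13% grade 4 thrombocytopenia. Finally, a site might shift visits sensibly, since a dose 2 on Day 22 would land on Follow-up Visit 1.

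All of this bears on size, and it is why the point is minor. It does not remove the gap. No section re-times the CBCs. Sections 12.6.1 and 12.6.2 refer to the last treatment and to later follow-up, but set no count dates. Unscheduled counts are allowed, but none is required.

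**Conclusion.** The concern holds, as a minor point held with moderate confidence. It is exact that a dose 2 delay of 4, 5 or 6 days leaves no permitted CBC day in the protocol's stated nadir, and that delays of 1 to 9 days leave neither nominal visit (Day 43 or 57) in it. The number of DLTs lost cannot be computed, because it depends on episode length, grade 3 lead-in and the frequency of late dosing, none of which the documents give. The nadir timing itself comes from ¹⁷⁷Lu-J591 studies and not from this combination. Across the assumed ranges the missed share runs from none to most of the short episodes in delayed patients. The escalation probability at a true DLT rate of 0.40 then moves from 0.31 to at most about 0.35. The MTD is unlikely to change for this reason alone, but the gap affects both the primary endpoint and patient safety.

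**What to change.** State in Section 6 and Table 15 that CBCs after dose 2 are timed from the actual date of dose 2, with the Visit 3 count aimed at day 30 after that dose and permitted on days 28–32. The efficacy visit can stay at Day 85.

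In the same model, with dose 2 on Day 22 and a 3-day lead-in (an unfavorable case), the missed shares of 5/7/10-day episodes are:

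| Visit 3 timing | Missed |
|---|---|
| As written (Day 43) | 100% / 87% / 25% |
| Any day 28–32 after dose 2 | 14% / 1% / 0% |
| Day 30 after dose 2 | 0% / 0% / 0% |

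Part of the gain for 5-day episodes comes from moving the target from day 28 to day 30 and tightening the window, and not from re-anchoring alone. That part also helps on-time patients, whose Visit 3 count may now be drawn on Day 40–42, before the nadir.

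The cost is a short amendment and a window of ±2 instead of ±3 days for one laboratory-only visit, which Section 6.1.2.3 allows at any CLIA-certified laboratory. It adds no draws and no patients.

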6.1 Schedule of Evaluations

Table 15: Schedule of trial events:

| | Screening | Treatment Visit 1 | Imaging visit | Treatment Visit 2 | F/U Visit 1 | F/U Visit 2 | F/U Visit 3 | F/U Visit 4 | F/U Visit 5 | Scan / Efficacy Visit | Short-Term F/U ^k | Long-Term F/U |
|--|-----------|-------------------|---------------|-------------------|-------------|-------------|-------------|-------------|-------------|-----------------------|-----------------------------|----------------|
| Informed Consent | x | | | | | | | | | | | |
| Demographics | x | | | | | | | | | | | |
| Medical History | x | x | x | x | x | x | | x | | x | x | |
| Physical Exam | x | x | x | x | x | x | | x | | x | x | |
| Performance Status | x | x | x | x | x | x | | x | | x | x | |
| Vital Signs ^a | x | x | x | x | x | x | | x | | x | x | |
| PRO ^l | x | x | x | x | x | x | | x | | x | x ^l | |
| CBC with diff, plts ^b | x | x | x | x ^c | x | x | x | x | x | x | x | |
| Serum Chemistry ^d | x | x | x | x | x | x | x | x | x | x | x | |
| PSA | x | x | | x | | x | | x | | x | x | |
| LDH | | x | | x | | x | | x | | x | x | |
| Testosterone | x | | | | | | | | | x | | |
| CTC Count ^e | x | x ^e | | | | | | | | x | | |
| CTC for Research ^f | x | x ^f | | | | | | | | x | | |
| Cell-Free DNA Research sample ^g | x | x ^g | | | | | | | | x | | |
| Immune research sample ^m | x | x ^m | | | | | | | | x | | |
| ⁶⁸ Ga-PSMA infusion & PET CT | x | | | | | | | | | x | | |
| Radiographic evaluation ^h | x | | | | | | | | | x | x ^h | x ^h |
| ¹⁷⁷ Lu-J591 infusion | | x | | x | | | | | | | | |
| ¹⁷⁷ Lu-PSMA-617 infusion | | x | | x | | | | | | | | |

| | | | | | | | | | | | | |
|---|---|---|----------------|----------------|---|---|--|---|--|---|---|---|
| ¹⁷⁷ Lu-Planar/SPECT imaging ⁱ | | | x ⁱ | x ⁱ | | | | | | | | |
| Archival Tissue | x | | | | | | | | | | | |
| Adverse Event Monitoring | | x | x | x | x | x | | x | | x | x | |
| Concurrent Medications | x | x | x | x | x | x | | x | | x | x | |
| Survival Assessment ^j | | | | | | | | | | | | x |

- a: Vital signs will include height and weight during screening and at least weight thereafter
- b: Any subject with grade >2 neutropenia or thrombocytopenia at any time point will be followed at least weekly until resolution to grade 1
- c: Any subject with grade ≥2 neutropenia or thrombocytopenia at Treatment 2 will initially not be eligible to receive the second ¹⁷⁷Lu-J591 / ¹⁷⁷Lu-PSMA-617 infusions. The dose will be held until the toxicity has resolved to grade 1 for a maximum of 2 weeks. If the toxicity has not resolved after 2 weeks, the dose will be discontinued.
- d: CMP (with direct bilirubin in subjects with known Gilbert’s syndrome)
- e: CTC enumeration via CellSearch methodology may be obtained during screening or prior to treatment C1D1
- f: CTC collection for research purposes may be performed during screening or prior to treatment C1D1: two 2.3% sodium citrate “light blue top” tubes
- g: Cell-Free DNA BCT[®] may be obtained during screening or prior to treatment C1D1 and will be whole blood collection in a tube intended for collection, stabilization and transportation of cell-free plasma DNA. 10 mL tube will be used for collecting whole blood for research purposes
- h: Radiographic evaluation will include bone scan, CT/MRI of abdomen/pelvis, and Chest x-ray (CXR waived if CT/MRI includes chest). Following mandatory repeat imaging with Scan/Efficacy visit, continued repeat imaging is recommended approximately 12 weeks until radiographic progression as part of standard care.
- i: Planar/SPECT imaging one week after the ¹⁷⁷Lu-PSMA-617 1st dose infusion in all subjects. Optional imaging will be performed on consenting subjects between D1-D4 and/or prior to treatment #2 on D15.
- j: Survival assessment and relevant medical history to be collected until death
- k: Short-term follow up to be completed q4 weeks following the scan visit until 6 months from the 1st treatment visit. Subjects who are progression-free at 6 months will continue with q4-week labs and q12-week standard imaging per guidelines (as in h above).
- l: PRO = patient reported outcomes = BPI-SF and FACT-P; to be performed at time points specified during treatment phase, then q12 weeks (at imaging time points) during short-term follow up until radiographic progression
- m: serum for immune assays; 1 sample to be collected at any time during screening prior to treatment #1, then again during scan/efficacy visit

